7.11 Analysis of Biomarker Data

For Part D and E:

- Plasma Galactitol, the analysis should evaluate maximum galactitol reduction (absolute change and percent change) defined as the lowest galactitol value on any of the following days of treatment (Day 1, Day 12, Day 32) vs. Galactitol level at baseline (calculated as a mean of 2 pre-dose measurements, such as Day -1 and Time-0 on Day 1 of dosing)
- Plasma Galactose, the analysis should evaluate the pre-dose galactose level on Day 12 and Day 32 vs. Galactose level at baseline (evaluated as a mean 2 pre-dose measurement, such as Day -1 and Time-0 on Day 1 of dosing)
- Whole blood Gal-1P the analysis should evaluate the pre-dose Gal-1P on Day 12 and Day 32 vs. Gal-1P level at baseline (evaluated as a mean 2 pre-dose measurement, such as Day -1 and Time-0 on Day 1 of dosing)

In addition, plasma galactitol changes will be analyzed based on below subgroup categories if data permit:

- Gender: Male / Female
- Age: $\langle 21 \text{ years } \rangle = 21 \text{ years and } \langle 30 \text{ years } \rangle = 30 \text{ years}$
- BMI: $<22 \text{ kg/m}^2 / 22-25 \text{ kg/m}^2 / >25 \text{ kg/m}^2$
- Enzyme activity: <0.1%, 0.1-0.4%, >0.4%

Urine galactitol levels will be provided as tabulated values and they will not be subjected to a formal analysis.

For genetic analysis, allele specific mutations will be reported as tabulated information

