- j: On Days 1, 6, 12, 13, 20, and 32, study drug will be administered at the clinic. All other doses of study drug will be taken at home QD with water in the morning (preferably after an overnight fast of ≥10 hours with the fast broken ≥2 hours after the dose). Study drug administration should be at approximately the same time of day (preferably 8 am) throughout the multiple dosing period. See [Section 6.7](#) for when study drug will be dispensed and/or collected.
- k: The 5-day washout between single and multiple dosing will start immediately after the Day 1 dose and end immediately before the Day 6 dose. There is no visit on Day 5; it is in the Schedule of Assessments only for depiction of the 5-day washout.
- l: For the Day 1 dose, blood samples for PK will be collected predose (within 60 minutes before the dose) and at 0.5, 1, 1.5, 2, 4, 6, 8, 12, 24, 36, and 48 hours (±5 minutes for all time points) after the dose. On Days 12 and 32, blood samples for PK will be collected predose (within 60 minutes before the dose) and at 0.5, 1, 1.5, 2, 4, 6, 8, and 12 hours (±5 minutes for all time points) after the dose. On Day 13, a blood sample for PK will be collected predose (i.e., at 24 hours ±5 minutes after the Day 12 dose). On Day 33, blood samples for PK will be collected at 24 and 36 hours (±5 minutes for both time points) after the Day 32 dose. On Day 34, a blood sample for PK will be collected at 48 hours (±5 minutes) after the Day 32 dose.

- m: For Cohort D3 only, urine for PK will be collected predose (spot collection within 60 minutes before the Day 1 dose) and in 4-hour intervals (0 to 4, >4 to 8, >8 to 12, >12 to 16, >16 to 20, and >20 to 24) through the first 24 hours after the Day 1 dose followed by 12-hour intervals (>24 to 36, >36 to 48, >48 to 60, and >60 to 72) from 24 to 72 hours after the Day 1 dose. Allowable windows for urine collection container changes will be \pm 30 minutes through the first 24 hours and \pm 1 hour thereafter.
- n: Cohort D3 = highest planned dose level cohort in Part D.
- o: With the exception of the blood samples for biomarkers taken at Screening and Day -1, the time points and allowable windows for the blood samples for biomarkers will match those for the blood samples for PK.

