7 STATISTICAL METHODS

7.1 General

The statistical analysis will be conducted following the principles specified in the International Council for Harmonization (ICH), formerly the International Conference of Harmonization, Topic E9 Statistical Principles for Clinical Trials (CPMP/ICH/363/96).

All statistical tabulations and analyses will be done using SAS®, Version 9.4 or higher.

Unless otherwise noted, for continuous outcomes, descriptive statistics will include the number of subjects, mean, 95% confidence interval (CI) for the mean, standard deviation (SD), median, minimum (Min), maximum (Max), 25th percentile, and 75th percentile. For categorical outcomes, the number and percentage of subjects will be presented. Descriptive statistics will generally be presented by AT-007 group. For summaries of continuous AT-007 PK concentration and parameter data, the coefficient of variation will also be presented.

In the data listings, study day relative to first dose of study drug may be presented. Study day relative to first dose will be calculated as: event date - first dose date (+ 1 if event day \geq first dose date).

For analyses of change from baseline, baseline will generally be defined as the predose assessment on Day 1 or Day -1, as scheduled. If this value is unavailable, the last non-missing value prior to dosing will be used.

All data from the CRFs, as well as any derived variables, will be presented in data listings.

For safety summaries, the unscheduled and repeat assessments will not be summarized; however, all results will be included in the data listing.

Unless otherwise noted, the analyses will be done by Parts and actual treatment/dose received.

Three sets of outputs will be created: One set for Part A, B, C, and D, one set for Part D Extension and one set for Part E(as detailed below). In creating tables in 3 sets, parts already completed can be analyzed earlier than the whole study has been completed.

| Study Part | Study Population | Design | Table |
|---------------------|---|---|---|
| Study 1 art | Study 1 opulation | Design | 1 abic |
| Part A | Healthy Adult Subjects | SAD | Parts A, B, C, and D will be |
| Part B | Healthy Adult Subjects | MAD (QD for 7 days) | summarized under 1 st set |
| Part C | Healthy Adult Subjects | MAD (QD for 7 days) | |
| Part D | Adult Subjects with CG | SAD, 5-day washout, MAD (QD for 27 days) | |

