7.4 Examination of Subgroups

For Parts D, E and D Extension, blood galactitol changes will be analyzed based on below subgroup categories if data permit:

- Gender: Male / Female
- Age: $\langle 21 \text{ years} / \rangle = 21 \text{ years and } \langle 30 \text{ years} / \rangle = 30 \text{ years}$
- BMI: $<22 \text{ kg/m}^2 / 22-25 \text{ kg/m}^2 / >25 \text{ kg/m}^2$
- Enzyme activity: <0.1%, 0.1-0.4%, >0.4%

Additionally forest plot will be displayed for Part D and E at Day 32 and for Part D extension at Day 90/EOT for blood galactitol results.

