7.5 Analysis Populations

Two analysis populations will be defined:

• Screened Population (SP): The screened population will consist of all subjects who are screened independent if they were eligible or not.

- Randomized Population: The randomized population will consist of all subjects who are randomized to any cohort.
- Safety Population: The safety population will consist of all subjects who are randomized and receive at least 1 dose of study drug. All analyses will be performed according to treatment received. This population will be used for all analyses of safety data and biomarker data.
- Pharmacokinetic Population: The PK population will consist of all subjects who receive at least 1 dose of AT-007 and have sufficient concentration-time data to estimate at least one of the planned PK parameters, as determined by the study Pharmacokineticist. This population will be used for all analyses of PK.

For Parts D and E, the safety and PK population may be defined separately for the SAD and MAD periods.

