| _ | Summary of AT-007 Amount Excreted in Urine – Part A (PK |
| Table 14.2.3a | Population) |
| Table 14 2 2 4 | Summary of AT-007 Amount Excreted in Urine – Part D (PK |
| Table 14.2.3d | Population) Summary of AT-007 Urine Pharmacokinetic Parameters – Part A |
| Table 14.2.4a | (PK Population) |
| | Summary of AT-007 Urine Pharmacokinetic Parameters – Part D |
| Table 14.2.4d | (PK Population) |
| Table 14.2.5c | Summary of CSF Concentration of AT-007 - Part C (PK Population) |
| T 11 1426 | Statistical Analysis of Dose Proportionality after Single dose - Part A |
| Table 14.2.6a | (PK Population) |
| T 11 142 (1 | Statistical Analysis of Dose Proportionality after Multiple dose – Part |
| Table 14.2.6b | B and Part C (PK Population) Statisfical Analysis of Dose Proportionality after Single dose. Part |
| Table 14.2.6d1 | Statistical Analysis of Dose Proportionality after Single dose – Part D (PK Population) |
| 14010 1 1.2.041 | Statistical Analysis of Dose Proportionality after Multiple dose – Part |
| Table 14.2.6d2 | D (PK Population) |
| | Statistical Analysis of Dose Proportionality after Multiple dose – Part |
| Table 14.2.6de | D Extension (PK Population) |
| | Statistical Analysis of Dose Proportionality after Single dose – Part E |
| Table 14.2.6e1 | (PK Population) |
| | Statistical Analysis of Dose Proportionality after Multiple dose – Part |
| Table 14.2.6e2 | E (PK Population) |
| Table 14.2.7.1.1d | Summary of Plasma Galactitol Results – Part D (Safety Population) |
| Table 14.2.7.1.2d | Summary of Plasma Galactose Results – Part D (Safety Population) |
| Table 14.2.7.1.3d | Summary of Whole blood Gal-1P Results – Part D (Safety |
| Table 14.2.7.1.1e | Population) Summers of Pleame Colectited Begulta - Part E (Sofety Perulation) |
| | Summary of Plasma Galactitol Results – Part E (Safety Population) |
| Table 14.2.7.1.2e | Summary of Plasma Galactose Results – Part E (Safety Population) Summary of Whole blood Gal-1P Results – Part E (Safety |
| Table 14.2.7.1.3e | Population) |
| 14010 1 1.2.7.1.30 | Plot of Mean (+/-SD) Plasma Galactitol Concentrations over Time – |
| Figure 14.2.7.1.1d | Part D (PK Population) |
| - | Plot of Mean (+/-SD) Plasma Galactose Concentrations over Time – |
| Figure 14.2.7.1.2d | Part D (PK Population) |
| F: 1407121 | Plot of Mean (+/-SD) Whole blood Gal-1P Concentrations over Time |
| Figure 14.2.7.1.3d | – Part D (PK Population) |

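### SAP 7.11 defines plasma galactitol change in Parts D and E only as a lowest on-treatment value against a two-sample mean, which leans toward a reduction when the drug does nothing, and it specifies no contrast with placebo

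*SAP*

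**What the plan says.** SAP 7.11 asks for the maximum plasma galactitol reduction, absolute and percent, "defined as the lowest galactitol value on any of the following days of treatment (Day 1, Day 12, Day 32"). Baseline is "calculated as a mean of 2 pre-dose measurements, such as Day -1 and Time-0 on Day 1 of dosing". The section defines no other galactitol change. For galactose in the same section, "the analysis should evaluate the pre-dose galactose level on Day 12 and Day 32" against the same kind of baseline, and Gal-1P follows that pattern.

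Protocol Appendix D, footnote o, says that apart from Screening and Day -1 "the time points and allowable windows for the blood samples for biomarkers will match those for the blood samples for PK". Appendix E, footnote m, says the same for Part E.

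Unless otherwise noted, SAP 7.1 says "descriptive statistics will include the number of subjects, mean, 95% confidence interval (CI) for the mean", and SAP 7.11 notes no exception. SAP 7.4 adds that a "forest plot will be displayed for Part D and E at Day 32". On populations, SAP 7.5 says of the Safety Population: "This population will be used for all analyses of safety data and biomarker data". That population includes placebo.

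**The concern.** The effect on galactitol is a secondary objective, and SAP section 4 keeps blood galactitol as a secondary endpoint. The lowest of many readings falls below the average of two readings through ordinary fluctuation alone. The report would print a mean maximum reduction with a 95% CI for each cohort, and that interval can exclude zero when nothing has happened. A reader who sees the active arm alone could take it for a drug effect.

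The definition also leaves a programmer to guess. If the minimum is taken across days, no Day 32 quantity exists for the Day 32 forest plot. If it is taken per day, the plotted quantity is a nine-sample minimum.

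**Working it through.** The plan states no figure to reproduce: no sample count, variability or power is given for galactitol.

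**Sample count** (Appendix D footnotes l and o; Appendix E footnotes l and m). Day 1 has 8 post-dose draws (0.5 to 12 h), with time 0 kept as baseline. Days 12 and 32 each have one pre-dose and 8 post-dose draws. Total 8 + 9 + 9 = 26; Day 32 alone, 9. Other readings give 27 (time 0 also counted) or 33 (draws at 24 h and later counted: 11 + 10 + 12).

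**Expected minimum, independent normal values.** E[min of k] = ∫ x·k·φ(x)·(1−Φ(x))^(k−1) dx. In within-subject SD units this is −1.49 for k = 9, −1.98 for 26, −2.00 for 27 and −2.08 for 33. The baseline mean has expectation 0, so these are also the expected changes with no drug effect. Whether 26, 27 or 33 is right matters little.

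**Simulation with within-day correlation.** Assumed, because the documents give neither: CV 3, 5, 10 and 20%; 0, 50, 80, 95 or 100% of variance shared within a calendar day; multiplicative or additive error; no drift. Baseline is the mean of Day -1 and Day 1 time 0, and time 0 shares the Day 1 effect. There were at least 80,000 subjects per scenario. The CI is a t interval on 4 subjects, counted when its upper limit is below zero. Mean falls are for multiplicative error; CI rates cover CV 3-20% and both error models.

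| Quantity, no drug effect | Mean fall, CV 5% | CV 10% | CV 20% | CI wholly below zero |
|---|---|---|---|---|
| 26-sample minimum, 95% to 0% shared | 6-9% | 11-18% | 20-32% | 46-92% |
| 26-sample minimum, 100% shared | about 4% | about 8% | 15-16% | 26-31% |
| Day 32 minimum, 95% to 0% shared | 2-7% | 3-14% | 5-25% | 6-68% |
| Day 32 minimum, 100% shared | none | none | none | as pre-dose Day 32 |
| Pre-dose Day 32 | none (0 to +2% over all CVs) | | | 2.4-3.5% |
| Day 32 0-24 h average | none (0 to +2% over all CVs) | | | 2.3-3.1% |

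Additive error gives slightly larger falls (26 samples: 11-19% at CV 10%, 22-38% at CV 20%). The CI rate hardly moves with CV, because the bias and its SD scale together: with nothing shared it runs from 86% at CV 3% to 92% at CV 20%. It depends mainly on within-day correlation.

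**Contrast with placebo.** The two arms have the same expected minimum under the null, so their difference is centred on zero if sampling is equally complete. With a constant true 50% reduction and multiplicative error, the difference of 26-sample minima is 50 × (1 − null fall):
- CV 5%: 50 × 0.94 = 47 to 50 × 0.91 = 45.5 (simulated 45-47 points)
- CV 10%: 50 × 0.89 = 44.5 to 50 × 0.82 = 41
- CV 20%: 50 × 0.80 = 40 to 50 × 0.68 = 34

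If error is additive, the difference reads 50-51.

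**Precision of the contrast.** 95% half-width = t × SD × √(1/n₁ + 1/n₂).
- 4 versus 6 (three cohorts): 2.306 × √(1/4 + 1/6) = 1.49
- 4 versus 2 (one cohort): 2.776 × √(1/4 + 1/2) = 2.40, about 1.6 times wider

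The null SD of the pre-dose Day 32 change is about 6.15, 12.35 and 25.15 points at CV 5, 10 and 20%. Half-widths are therefore about 9, 18 and 37 points (4 versus 6) and about 15, 30 and 60 points (4 versus 2). The 26-sample minimum is narrower: its null SD is 7.1-7.7 at CV 10% and 12-14 at CV 20%, giving about 11 and 17-21 points for 4 versus 6. The Day 32 average gives 13-16 and 26-32.

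**The case against.** The strongest reply is that SAP 7.11 openly calls the quantity a maximum reduction, which is a legitimate pharmacodynamic measure. Biomarker summaries are descriptive (Protocol 9.2.9), no test is planned, and efficacy analysis is marked not applicable (Protocol 9.2.10). Placebo subjects are in the galactitol tables and listings, and anyone with the listings can derive a pre-dose change. A placebo contrast of the existing minimum is centred on zero under the null and narrower than one based on pre-dose Day 32.

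Much of this stands. The minimum deserves to be kept, and its contrast is worth reporting. The 2.5% benchmark is how often a correctly centred interval would lie below zero, not the error rate of a planned test. What does not go away is that the plan prints a within-arm CI for a quantity that is not centred on zero, specifies no contrast, and gives galactitol no fixed-time change although its neighbours have one.

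Three stronger readings are tempting and are not supported:
- That half to nine-tenths of null cohorts would show a false reduction. This needs the across-days reading and less than fully shared within-day variation. The text settles neither, and the upper end needs no correlation between draws 30 minutes apart.
- That this statistic drives dose decisions. The documents bring galactitol results into escalation but do not say that they are summarised this way.
- That nothing else will be shown. The table titles are general, and SAP section 8 lists a "Plot of Mean (+/-SD) Plasma Galactitol Concentrations over Time". Those figures show concentrations rather than change and are labelled for the PK Population, which leaves out subjects who received only placebo.

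**Conclusion.** The concern holds and should be fixed. The direction of the bias is certain for the across-days minimum. It is certain for the Day 32 minimum unless all variation is shared within the day. Its size is not known, because it rests on an assumed CV, and the false-exclusion rate rests mainly on an assumed within-day correlation. Over the assumed range that rate is about 26-92% for the across-days minimum and about 2.5-68% for the Day 32 minimum, against about 2.5-3.5% for a fixed pre-dose Day 32 change. Placebo carries the same bias, so the within-arm figure can be interpreted only beside placebo. With two placebo subjects per cohort, comparison by eye within a cohort is weak.

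**What to change.** In SAP 7.11:
- Add the absolute and percent galactitol change at pre-dose Day 12 and pre-dose Day 32, optionally with the Day 32 0-24 h average (ten draws, the last on Day 33).
- Name one Day 32 quantity and use it in the subgroup tables and forest plot.
- Keep the maximum reduction as a labelled summary, state whether it is per day or across days, and say that its within-arm CI is not evidence of effect.
- Show every galactitol change, including the minimum, by dose beside pooled placebo (SAP 7.12.1 already pools placebo for safety), with a descriptive difference and CI. Note that the contrast of minima understates a real effect if error is multiplicative.
- State that precision depends on the number of cohorts, since Part E may have only one, and that the intervals ignore subjects who re-enter cohorts (Protocol 4.4).
- Reconcile the biomarker population so that placebo is shown: Protocol 9.2.2 assigns biomarkers to the PK population, SAP 7.5 to the Safety Population, and the mean-over-time figures are labelled PK Population.
- Date and disclose the change, because the Sponsor/CRO is unblinded in Parts D and E (Protocol 5.2) and Cohorts D1 and D2 are complete.

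The cost is SAP wording and reprogramming of Tables 14.2.7.1.1d/e, the eight subgroup tables (14.2.7.2 to 14.2.7.5, d and e) and Figures 14.2.7.2d/e, plus a population label on Figures 14.2.7.1.1d/e. No new data are needed. The drawbacks are that pre-dose values measure trough rather than maximum effect, their contrasts are wide, the displayed reduction will probably be smaller, and a late choice made unblinded carries a selection risk that disclosure reduces but does not remove.

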7.12 Analysis of Safety Data

7 12 1 General

The evaluation of safety will be based on the occurrence of treatment-emergent adverse events (TEAEs); discontinuations from study drug and/or the study because of AEs; clinical laboratory test results, physical examination findings, vital sign evaluations, and 12-lead ECGs results. All safety endpoints will be summarized descriptively. No statistical inference will be applied to the safety endpoints. Descriptive statistics will be calculated for quantitative safety data and frequency counts will be compiled for classification of qualitative safety data.

Safety measures including the baseline data will be summarized descriptively within each part (Parts A, B, C, D, E and D Extension) of the study by each cohort (dose level of AT-007 and placebo), pooled AT-007 group, and pooled placebo group.

For analyses of change from baseline, baseline will generally be defined as the predose assessment on Day 1 or Day -1, as scheduled. If this value is unavailable, the last nonmissing value prior to dosing will be used. Otherwise, missing observations will be treated as missing at random, and no data imputation will be performed. All data from the eCRFs, as well as any derived variables, will be presented in data listings.

7.12.2 Adverse Events

All AEs will be coded to system organ class (SOC) and preferred term (PT) using MedDRA, Version 22.0 or later, and presented by subject data listings.

A treatment-emergent AE (TEAE) is defined as an AE that is not present prior to cohort with investigational product, but appeared following cohort or was present at cohort initiation but worsened during cohort. An AE that was present at cohort initiation but resolved and then

reappeared while the subject was on cohort is a TEAE (regardless of the intensity of the AE when the cohort was initiated). Programmatically, an AE will be classified as a TEAE if the start date and time occurs on or after the start date and time of first investigational product dosing.

The TEAE will be assigned to treatment based on the start date/time of occurrence.

The overall incidence of TEAEs (number and percentage of subjects) as well as the number of events will be summarized by cohort, severity grade, SAEs, causally related TEAE and SAEs, TEAEs leading to study or treatment discontinuation, life-threatening SAEs, and SAEs resulting in death.

The TEAEs will be summarized and tabulated at both the subject (number [%] of subjects) and event (number of events) level:

- By cohort, SOC, and PT
- By cohort, SOC, PT, and maximum reported severity
- By cohort, SOC, PT, and closest relationship to study drug

For the incidence at the subject level by SOC and PT, if a subject experiences more than 1 event within the same SOC and PT, only 1 occurrence will be included in the incidence.

For the incidence at the subject level by SOC, PT, and severity, if a subject experiences more than 1 event within the same SOC and PT, only the highest severity grade will be included in the incidence.

For the incidence at the subject level by SOC, PT and relationship to study drug; if a subject experiences more than 1 event within the same SOC and PT, only the most closely related occurrence will be included in the incidence.

Any SAEs, AEs with outcome of deaths, or AEs resulting in discontinuation of study or cohort will be presented.

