7.1. Safety Assessments

7.1.1. Adverse Events

AEs will be monitored throughout the study. AEs will be collected for each subject from the time of informed consent through the EOS (or EOE) Visit. Subjects will be queried in a nonleading manner, without specific prompting (e.g., “Has there been any change in your health status since your last visit?”).

Safety reporting requirements are provided in [Section 8](#).

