8. ADVERSE EVENTS

Subjects will be monitored for AEs from the signing of informed consent through the EOS (or EOE) Visit. The Investigator or a medically qualified designee will review each event. The Investigator or designee will assess its relationship to the study drug. Each AE will be graded for severity, and the date and time of onset and cessation will be recorded along with any treatment given for the AE and any action taken with regard to the study drug. Treatment of any AE will be evaluated and managed by a physician, either at the study site or at a nearby hospital or emergency room, as appropriate. The AE resolution or outcome will be recorded. All non-serious AEs will be reported on a regular basis or as specified by the Sponsor.

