8.1. Definitions

8.1.1. Adverse Event (AE)

An AE is defined as any untoward medical occurrence associated with the use of a drug in humans, whether or not considered drug related.

An AE can be any unfavorable and unintended sign (e.g., an abnormal laboratory finding), symptom, or disease temporally associated with the use of a drug, without judgment to causality. An AE can arise from any use of the drug (e.g., off-label, use in combinations with another drug) and from any route of administration, formulation, or dose, including an overdose. AEs may include the onset of new illness and the exacerbation of pre-existing conditions. New signs and symptoms of underlying disease, or signs and symptoms of emerging disease must be recorded as AEs.

The Investigator/designee should attempt to establish a diagnosis of the event based on signs, symptoms, and/or other clinical information. In such cases, the diagnosis should be documented as the AE and not the individual signs/symptoms.

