8.1.2. Serious Adverse Event (SAE)

A SAE is an AE that meets one or more of the following criteria:

- Results in death
- Is life-threatening (i.e., a subject is at immediate risk of death at the time of the event, not an event where occurrence in a more severe form might have caused death)
- Requires hospitalization or prolongation of existing hospitalization
- Results in persistent or significant disability or incapacity
- Is a congenital anomaly or birth defect
- Is an important medical event that may jeopardize the subject or may require a medical or surgical intervention to prevent one of the outcomes listed above

Examples of “important medical events” that are SAEs include allergic bronchospasm requiring intensive treatment in an emergency room or at home, blood dyscrasias, or convulsions that do not result in in-patient hospitalization.

The term "severe" is often used to describe the severity of a specific event (as in mild, moderate, or severe); the event itself, however, may be of relatively minor medical significance (such as severe headache). This is not the same as "serious," which is based on subject/event outcome or action criteria usually associated with events that pose a threat to a subject's life or functioning as defined by the criteria above.

During the study, if a subject has a hospitalization or procedure (e.g., elective surgery) that was scheduled before the study entry (i.e., before informed consent for an event/condition that occurred before the study), then the hospitalization is considered a therapeutic intervention and not the result of a SAE. However, if the event/condition worsens during the study, it should be reported as an AE (or SAE, if the event/condition results in a serious outcome such as prolongation of hospitalization).

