9.2.7. Safety Analyses

The evaluation of safety will be based on the occurrence of treatment-emergent adverse events (TEAEs); discontinuations from study drug and/or the study because of AEs; clinical laboratory test results, physical examination findings, vital sign evaluations, and 12-lead ECGs results. All safety endpoints will be summarized descriptively. No statistical inference will be applied to the safety endpoints. Descriptive statistics will be calculated for quantitative safety data and frequency counts will be compiled for classification of qualitative safety data.

AEs will be coded by SOC and PT using MedDRA, version 22.0 or higher.

TEAEs are defined as AEs with onset on or after the date/time of the first dose of study drug.

Safety analyses will be described in detail in the SAP.

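### The SAP defines worsening AEs as treatment-emergent but programs the flag on start date alone, so a pre-dose AE kept in one record that worsens is missing from the TEAE tables

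*SAP*

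**What the plan says.** SAP 7.12.2 opens with a prose definition. An AE is treatment-emergent if it is new, if it "was present at cohort initiation but worsened during cohort", or if it was present at the start, resolved and came back. The programming rule that follows has no severity term: "Programmatically, an AE will be classified as a TEAE if the start date and time occurs on or after the start date and time" of the first dosing with investigational product. Assignment to treatment also uses timing only: "The TEAE will be assigned to treatment based on the start date/time of occurrence".

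Protocol 9.2.7 is narrower than the SAP prose: "TEAEs are defined as AEs with onset on or after the date/time of the first dose of study drug". Worsening is not mentioned there. SAP section 4, which lists changes from the protocol, does not mention the wider definition.

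On collection, protocol 7.1.1 states: "AEs will be collected for each subject from the time of informed consent through the EOS (or EOE) Visit". Section 8 adds that "the date and time of onset and cessation will be recorded" for each AE. SAP 3.2.1 lists one start, one stop and one severity category among the details collected. Protocol 8.1.1 says that "AEs may include the onset of new illness and the exacerbation of pre-existing conditions".

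**The concern.** The two SAP rules stand next to each other and cannot both be followed. A programmer who implements the rule as written will not flag an event that the definition includes. AEs are collected from consent, so records with a pre-dose start will exist, and some may still be open at dosing. Neither document says that a rise in severity closes one record and opens another.

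The primary endpoints are overall safety and AEs (SAP 2.4), and SAP 7.12.1 names TEAE occurrence first among the bases of the safety evaluation. The groups are very small, so one subject on the wrong side of the flag changes an incidence visibly.

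The anchor raises a second question. The definition is framed by cohort, but the program refers to first dosing without saying whether that means first in the study or first in the cohort. Subjects in Parts D and E may re-enter a further cohort after a washout of at least 5 days (protocol 4.4), and Part D subjects may enter the Extension (protocol 3.3.6).

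**Working it through.** The plan states no TEAE count or rate, so there is no figure of its own to reproduce. The check is logical, followed by a simple size calculation.

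**Step 1. The two rules.** Let s be the recorded AE start and d the first dose.
- Prose: TEAE if s ≥ d, or if the event was present at d and worsened afterwards, or if it was present at d, resolved and reappeared.
- Program: TEAE if s ≥ d.

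**Step 2. Apply both to five record types.**

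| Record | Prose | Program |
|---|---|---|
| New onset after dosing | TEAE | TEAE |
| Starts between consent and first dose, one record, worsens after dosing | TEAE | not a TEAE |
| Pre-existing condition, exacerbation entered as a new AE when it worsens | TEAE | TEAE |
| Present at start, resolved, recorded again on reappearance | TEAE | TEAE |
| Starts before dosing, unchanged | not a TEAE | not a TEAE |

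The rules agree on 4 of 5 types. Only the second is lost from the TEAE tables.

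**Step 3. Can the second type occur?** Protocol 6.2 allows screening up to 28 days before first dose in Parts A to C, 40 days in Parts D and E, and 60 days in the Extension (SAP 3.1.2.1 has 40 for the Extension). An AE can start in that window and be open at dosing. If the site then raises the severity on the existing record, s stays before d and the program does not flag it.

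**Step 4. The anchor, under each reading, for a subject in a later cohort or the Extension.**
- First dose in the study: an event that starts after the earlier cohort but before dosing in the later one satisfies s ≥ d and is flagged. An event that starts during the earlier cohort and worsens at the later dose stays with the earlier treatment, because assignment follows the start.
- First dose in the current cohort: the extra flagging disappears. An event carried over in one record that worsens is not a TEAE in the later cohort, which is the Step 2 gap again.

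**Step 5. Size.** For one subject with no other TEAE, the shift in incidence is 100/n percentage points. Group sizes are the planned ones in protocol 3.3 and SAP 3.1.4.
- Active cohort of 4 (Part D, Part E, B2, B4): 100/4 = 25
- Active cohort of 6 (Part A, B1, B3): 100/6 = 16.7
- Placebo, 2 per cohort: 100/2 = 50
- Part D active, pooled, 3 × 4 = 12: 100/12 = 8.3
- Extension active: 100/21 = 4.8 (protocol) or 100/12 = 8.3 (SAP)

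**The case against.** A reader might infer that the tables will systematically miss worsening of the chronic neurological complications of Classic Galactosemia, the harm one would most want to see. The documents do not support that. Those complications predate consent and belong in medical and neurological history (protocol 9.2.6). Protocol 8.1.1 makes an exacerbation an AE in its own right. Protocol 8.1.2, writing about hospitalizations or procedures planned before consent, says "However, if the event/condition worsens during the study, it should be reported as an AE". Entered that way, the event has a post-dose onset and is counted. This part of the objection stands.

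A reader might also infer that, for re-entrants and Extension subjects, every pre-dose event in the later cohort is counted as emergent. That holds only under the first-dose-in-study reading. The surrounding prose is framed by cohort, analyses are run by Part (SAP 7.1), and Appendix F of the protocol anchors Day 1 to the first Extension dose. It is an ambiguity, not an established over-count. Re-entry within Parts D and E also requires that the earlier cohort raised no safety or tolerability issue, which limits how often it matters. The Extension bars only discontinuation for a related TEAE.

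Three further points carry weight:
- The programmed rule agrees with protocol 9.2.7, so narrowing the SAP prose would also remove the contradiction.
- A separate data management plan governs eCRF processing (SAP section 5). It is not available here and may already require a new record on worsening.
- Nothing disappears from the report. All AEs are listed; SAEs, deaths and AEs leading to discontinuation are shown separately; laboratory, vital sign and ECG changes have their own summaries. Dose decisions rest on Safety Review Committee review and dose-limiting toxicities, not on the TEAE flag.

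These points reduce the consequence. They do not reconcile two incompatible rules in the same SAP section, and the exacerbation provisions do not say what to do with an AE already open from screening.

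**Conclusion.** The point holds in a limited form. SAP 7.12.2 is wrong as written: the program omits from the TEAE tables an AE that the definition includes, when it starts between consent and first dose, stays in one record and worsens after dosing. The anchor is separately ambiguous for subjects with more than one cohort or with Extension participation. I rate the severity as moderate, because the omission is confined to one record type and to summary tables with no inference attached.

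How often this would happen cannot be estimated from the documents. The 25-point and 8.3-point figures are the weight of a single subject, not an expected error. They assume that the subject has no other TEAE, that cohorts enroll as planned, and that the 12 pooled active Part D subjects are counted once each. The omission itself assumes that no unseen data-entry instruction already forces a new record on worsening.

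**What to change.** 1. Instruct sites that any increase in severity after dosing is entered as a new AE record with its own start date. For cohorts already completed, query or review AEs with a pre-dose start that were ongoing at dosing.
2. Define the TEAE anchor as the first dose in the current cohort or part.
3. Make the programmed rule match the definition, using dated severity where it exists. Code alone will not do this: with one severity category per record, a maximum severity after dosing cannot be derived.
4. Align protocol 9.2.7 with the SAP definition, or list the wider definition as a change in SAP section 4.

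The cost is a CRF completion instruction, a short data review for the completed cohorts, a small change to the derivation, and a text edit to the SAP (and to the protocol, if that route is chosen). No design change or additional subject is needed.
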